### 3.3. Study Definitions and Defined Variables

The baseline value will be defined as the last value obtained prior to the first vaccination. Individual antibody endpoint titers will be reported with values of  $C^*2^k$ , where  $k=0, 1, 2, \dots$

and C may vary depending on the dilutions used for a given assay. Values below each assay's limit of detection will be imputed as one-half the limit of detection. For analysis, the geometric mean of replicates for each sample will be computed and used as the response for all subsequent calculations, where applicable.

Immune response over time will be assessed by the positive incremental area under the curve (AUC) based on a graph with the analysis value (e.g., log endpoint titer) on the y-axis and visit week on the x-axis.

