## 5.5. Missing and Outlier Data

All attempts will be made to collect all data per protocol. Frequencies of missingness for primary outcomes will be calculated overall and within each study group. Less than 10% missing data that are missing completely at random will be considered ignorable missingness and complete case analysis will be utilized. No imputation will be performed for missing values. Data visualizations such as boxplots, histograms, or scatter plots will be used to identify outliers. Single outliers may be identified if values are outside of 1.5x the interquartile range depending on normality assumptions. Outliers will not be excluded from the primary analyses. Outliers identified during the analysis will be discussed in the analysis report.

Measurements that occur outside of study visit windows may be considered missing in sensitivity analyses. Table S5 provides an overview of each study visit along with the visit window upper and lower bounds, as specified in the study protocol.

Table S6. Analysis Time Windows

Visit	Visit day (visit window in days)	Lower bound (days)	Upper bound (days)
Screen	-45 to -3	-45	-3
Visit 1 (V1)	1	1	1
Visit 2 (Safety & Immun)	15 ( $\pm 3$ )	12	18
Visit 3 (V2)	29 ( $\pm 7$ )	22	36
Visit 4 (Safety & Immun)	43 ( $\pm 3$ )	40	46
Visit 5 (V3)	57 ( $\pm 7$ )	50	64

Visit	Visit day (visit window in days)	Lower bound (days)	Upper bound (days)
Visit 6 (Safety & Immun)	58-59	58	59
Visit 7 (Safety & Immun)	64 ( $\pm 3$ )	61	67
Visit 8 (Safety & Immun)	71 ( $\pm 3$ )	68	74
Visit 9 (Safety & Immun)	169 ( $\pm 7$ )	162	176
Visit 10 /Exit 4 (Safety & Immun)	337 ( $\pm 7$ )	330	344
Phone Follow-up 1 (MAAE)	365 ( $\pm 7$ )	358	372
Phone Follow-up 2 (MAAE)	393 ( $\pm 7$ )	386	400

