Total immune responses over time will be assessed by the positive incremental area under the curve (AUC). An AUC curve will be constructed with raw, unlogged endpoint titers on the y-axis and visit week on the x-axis (week 0 to week 48). AUC will be logged after calculation from raw values. For comparability between participants with different numbers of samples (visits) available, these values will be scaled (normalized) by the week of the last available sample. If no sample is available for visits other than the first and last, no explicit imputation will be done, and the AUC will be calculated based on available samples. Log AUC will be analysed similarly to the visit-by-visit titers and presented as mean AUC and 95% CI.

The magnitude of CD4+ and CD8+ T-cell effector function and polyfunctionality will be evaluated through response by cytokines such as IFN- $\gamma$  and IL2. The frequencies of CD4 or CD8 T cells responding to each test antigen with IFN- $\gamma$  and/or IL2 will be calculated using the following categories: all IFNy+, all IL2+, IFNy and IL2+, IFNy or IL2+. Descriptive statistics will evaluate the distribution of CD4+ and CD8+ responses and polyfunctionality scores by vaccination group and visit. Differences in CD4+ and CD8+ responses between vaccination groups at each visit will be evaluated using Kruskal-Wallis tests, and pair-wise comparisons of

particular visits will be performed with two-sided Mann-Whitney U test, with a Bonferroni-Holm step-down for adjusting p-values for multiple comparisons.

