## 8.2. Additional Immunogenicity Analyses

Further immunogenicity analyses (see Section 3.2.3 for planned sets of assays) will be considered exploratory for testing purposes (see Section 5.8 for how significance and multiplicity will be handled), but they will otherwise follow a similar process as the primary immunogenicity analysis. Secondary immunogenicity endpoints will entail primarily descriptive analyses. In general, continuous outcomes will be assessed using summary statistics such as the mean, median, standard deviation and IQR. Binary responses will be described using frequencies and percentages. Changes from baseline may be assessed within groups using paired t-tests (or Wilcoxon signed rank as appropriate) or McNemar's test for binary outcomes. For assays that are not conducted via titer experiments, the analysis values will be handled as log GMTs, after appropriate transformation of the data to be approximately normal when necessary; boxplots will show the assay values for each group, by visit.

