gp120 A244gD-D11	xx	xx.x (xx.x, xx.x)	xx	xx.x (xx.x, xx.x)	xx	xx.x (xx.x, xx.x)	0.xx
gp120 MNgD- D11	xx	xx.x (xx.x, xx.x)	xx	xx.x (xx.x, xx.x)	xx	xx.x (xx.x, xx.x)	0.xx
[Additional antigens]							

Note: N = Number of participants in the Immunogenicity Population; n = Number of participants with available analysis values ·ANOVA used to compare mean log AUC across all vaccination groups

**Table 15: Immunology Geometric Mean Titers and Associated 95% CIs by Visit, Antigen, and Vaccination Group – [assay name]**

Visit	Antigen	200 µg ALFQ (N=X)		100 µg ALFQ (N=X)		50 µg ALFQ (N=X)		p-value
		n	GMT (95% CI)	n	GMT (95% CI)	n	GMT (95% CI)	
Baseline (Day 0)	gp120A244gD-D11	xx	xx.x (xx.x, xx.x)	xx	xx.x (xx.x, xx.x)	xx	xx.x (xx.x, xx.x)	0.xx
	[Additional antigens]	xx	xx.x (xx.x, xx.x)	xx	xx.x (xx.x, xx.x)	xx	xx.x (xx.x, xx.x)	0.xx
		xx	xx.x (xx.x, xx.x)	xx	xx.x (xx.x, xx.x)	xx	xx.x (xx.x, xx.x)	0.xx
[Additional visits or Peak]		xx	xx.x (xx.x, xx.x)	xx	xx.x (xx.x, xx.x)	Xx	xx.x (xx.x, xx.x)	0.xx

[figure not shown]
**Note:** This will be adapted for assays with continuous analysis values, as appropriate

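### SAP 8.1 logs an incremental AUC that is zero for anyone who never exceeds baseline, and gives no rule for that case

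*SAP*

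**What the plan says.** SAP 8.1 assesses the total response over time by a positive incremental AUC from week 0 to week 48, scaled by the week of the last available sample. On the scale it says "An AUC curve will be constructed with raw, unlogged endpoint titers on the y-axis" and then "AUC will be logged after calculation from raw values". Log AUC is to be analysed in the same way as the by-visit titers. The note to Table 14 in Appendix 1 names the test: "ANOVA used to compare mean log AUC across all vaccination groups". That table's n counts participants who have an analysis value.

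SAP 3.3 takes the last value before the first vaccination as baseline. For undetectable titers it says "Values below each assay's limit of detection will be imputed as one-half the limit of detection". It gives no corresponding rule for the AUC.

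Two other places define the AUC on a different scale. Protocol 9.6.3 puts log titer on the y-axis, and SAP 3.3 gives log titer as its example. Neither calls for a second log.

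On missing data, SAP 5.5 says "No imputation will be performed for missing values", and SAP 5.3.2 limits the Immunogenicity Population to those with the data needed for the endpoint in question. On the exploratory assays, SAP 8.2 says "they will otherwise follow a similar process as the primary immunogenicity analysis".

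**The concern.** An incremental AUC counts only area above baseline, so its lowest possible value is 0. Section 8.1 logs that quantity without an offset, a floor or any rule for zero. The participants concerned are those with the weakest responses.

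If their log AUC becomes a missing value, Table 14 compares the arms after removing people because of a result seen after vaccination. The arm with the most such participants loses the most low values. In a trial meant to choose an adjuvant dose, a weaker dose could then look level with a stronger one on AUC, which is a named part of a secondary endpoint. It would also sit badly with the intention-to-treat principle in SAP 5.3.

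**Working it through.** **Inputs.** From the documents: visits at weeks 0, 2, 4, 6, 8, 10, 24 and 48 (SAP 8.1); undetectable values set to half the detection limit (SAP 3.3); 20 per arm and SD 0.2 for peak log titer (Protocol 9.4); two-sided 5% tests (SAP 5.7). Assumed, because the documents give no values: a detection limit (LOD) of 100, the titer profiles, and all response rates. Section 8.1 does not name the reference level of the increment; I take it to be baseline.

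**The plan's own figure.** The only immunogenicity power figure is 0.802, for peak titer (Protocol Table 11, n = 20, effect 0.202). It reproduces: with arm means −0.101, 0 and 0.101, the noncentrality is 20 × (0.101² + 0.101²) / 0.2² = 10.2, and the F test on 2 and 57 degrees of freedom has power 0.8017. There is no planned figure for the AUC, and nothing below depends on this one.

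**Step 1: what the formula returns.** Take titer minus week-0 titer, sum the positive trapezoids, divide by 48, then take log10.

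| Profile (LOD = 100) | Incremental AUC / 48 | log10 |
|---|---|---|
| Flat at 50 (LOD/2) throughout | 0 | undefined |
| Baseline 200, never above 200 | 0 | undefined |
| 50 throughout except 100 at week 10 | 50 × (2/2 + 14/2) / 48 = 8.33 | 0.92 |
| Responder: 50, 100, 100, 6400, 3200, 25600, 3200, 800 | 292,450 / 48 = 6093 | 3.78 |

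In the first row every increment is 50 − 50 = 0, whatever the LOD. With log titer on the y-axis, as in Protocol 9.6.3, the same profile also gives 0, but no further log is taken and 0 is a usable value.

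**Step 2: what the tests do.** With one log(0) held as minus infinity, the arm mean is minus infinity and ANOVA returns no result. Kruskal-Wallis still runs and ranks that participant lowest. If the software has already turned log(0) into a missing value, neither test sees the participant.

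**Step 3: how often a zero would occur.** If a fraction r of participants have zero AUC, the expected number among 60 is 60r, and the chance of at least one is 1 − (1 − r)^60.

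| r (assumed) | 0% | 1% | 2% | 5% | 10% | 20% |
|---|---|---|---|---|---|---|
| Expected zeros | 0 | 0.6 | 1.2 | 3 | 6 | 12 |
| P(at least one) | 0 | 0.45 | 0.70 | 0.95 | 0.998 | 1.00 |

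**Step 4: effect on the three-arm comparison.** 3,000 simulated trials per row, 20 per arm, responders identical in all arms (log10 mean 3.0, SD 0.2), zeros either dropped or placed at a floor of log10(50) = 1.70. Entries are rejection rates.

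| Response, 200/100/50 µg (assumed) | ANOVA, zeros dropped | ANOVA, zeros at floor | Kruskal-Wallis, zeros kept |
|---|---|---|---|
| 100/100/100% | 5.3% | 5.3% | 5.0% |
| 100/97.5/95% | 5.3% | 6.5% | 5.3% |
| 100/95/90% | 5.5% | 13.7% | 7.2% |
| 100/90/80% | 5.5% | 33% | 15% |

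In the last row the mean difference between the 200 and 50 µg arms is 0.00 with zeros dropped, and 0.20 × (3.0 − 1.70) = 0.26 with the floor. The floored ANOVA depends on the floor chosen. The rank test does not, as long as zeros rank lowest.

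**Step 5: two arms with heavy non-response.** 20 per arm, responder SD 0.3. A t-test among those with positive AUC rejects in about 5% in each scenario. A rank test with zeros kept rejects in about 43% (60% vs 30% response), 62% (80% vs 40%) and 38% (90% vs 60%). At 100% vs 95% the rank test gives 6.0% and the t-test 5.1%; at 100% vs 90%, 8.2% and 4.9%.

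**The case against.** A reader might infer that the SAP removes non-responders and compares the arms among responders only. The documents do not support that reading.

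- **Exclusion is never written.** The no-imputation rule concerns values that were not obtained, whereas a zero AUC is observed. SAP 10 allows SAS or R, so what happens to log(0) is not fixed, and a failed ANOVA would be noticed.
- **Zero AUC is not non-response.** SAP 8.1 leaves positivity to laboratory input. A non-responder with one small rise stays in, while a participant with a raised baseline can score 0.
- **Rank tests are already in the plan.** SAP 8.1 has a Kruskal-Wallis fallback and pairwise Mann-Whitney tests, and SAP 5.1 sends non-normal data to rank tests.
- **Other analyses keep these people.** By-visit and peak titers hold them at half the detection limit, and response rates are compared by Fisher or chi-squared tests. In the three heavy non-response scenarios of step 5, Fisher's exact test alone rejects in 35%, 65% and 49%.
- **Those scenarios have no source in the documents.** They fit poorly with gp120 IgG after up to three adjuvanted doses. Immunogenicity is secondary and described mainly by summary statistics.

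All of this limits the damage to the AUC comparison. It does not repair that comparison. The Table 14 shell names ANOVA, and the rank fallback helps only if zeros are kept, which no section says. Choosing an offset once the zeros are known would be a decision made after seeing data.

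**Conclusion.** The point holds for the AUC analysis alone. As written, SAP 8.1 applies a log that is undefined for any participant who never exceeds baseline, and the half-limit rule cannot prevent this. The test named in Table 14 must then omit those participants or fail. Omission is the likely default given SAP 5.3.2, SAP 5.5 and the Table 14 count, but that is an inference about how the analysis would be run, not a stated exclusion.

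The size depends on a zero-AUC rate that the documents do not give. It is nil when there are no zeros and near nil if almost all participants respond on gp120 IgG. It becomes material when zeros differ between arms: at an assumed 100/90/80% response, 5.5% rejection with zeros dropped against 15% with zeros ranked. It could be larger for the exploratory assays, but only if the similar process in SAP 8.2 is meant to include the AUC, which that section does not say. A hidden dose difference across the whole immunogenicity evaluation does not follow, because the titer and response-rate analyses retain everyone concerned.

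**What to change.** In SAP 3.3 and 8.1, keep the incremental AUC and state that participants with a zero AUC stay in the analysis, by one of two routes fixed before unblinding:

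- Set a pre-specified positive floor before logging, for example the area implied by one detection limit. Raise every smaller value to the floor as well. With LOD = 100, a rise of one limit held throughout gives 100 × 48 / 48 = 100, which is above the 8.33 of the single two-fold rise in the table; flooring the zeros alone would place them above that participant.
- Or, whenever any zero occurs, compare AUC by Kruskal-Wallis and Mann-Whitney with zeros tied at the lowest rank.

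Reconcile the y-axis scale between SAP 8.1 (raw titer) and Protocol 9.6.3 and SAP 3.3 (log titer). If log titer without a second log is adopted, zero is already a valid value. State in SAP 8.2 whether the AUC applies to the exploratory assays. Add the number of zeros per arm to Table 14, with a note that n includes them.

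The cost is a few sentences and one table note; SAP 11 already provides for an update before unblinding. The downside is that the floor value is a convention and affects the ANOVA result. Logging the total AUC would also avoid zeros, but it would replace the incremental endpoint that both documents define, so it is not proposed.

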## 8.2. Additional Immunogenicity Analyses

Further immunogenicity analyses (see Section 3.2.3 for planned sets of assays) will be considered exploratory for testing purposes (see Section 5.8 for how significance and multiplicity will be handled), but they will otherwise follow a similar process as the primary immunogenicity analysis. Secondary immunogenicity endpoints will entail primarily descriptive analyses. In general, continuous outcomes will be assessed using summary statistics such as the mean, median, standard deviation and IQR. Binary responses will be described using frequencies and percentages. Changes from baseline may be assessed within groups using paired t-tests (or Wilcoxon signed rank as appropriate) or McNemar's test for binary outcomes. For assays that are not conducted via titer experiments, the analysis values will be handled as log GMTs, after appropriate transformation of the data to be approximately normal when necessary; boxplots will show the assay values for each group, by visit.

## 8.3. Immunogenicity Sensitivity Analyses

Primary immunogenicity analyses conducted in the immunogenicity population may be repeated in the per-protocol population if per-protocol conditions are met. Results of primary analyses will be considered to be robust if effects are similar.

Examples of per-protocol sensitivity analyses include excluding study visits occurring out-of window, or where a major protocol deviation occurred. Bayes factors may be calculated and assessed for sensitivity analyses assessment.

If imbalance in participant demographic or clinical factors is detected between vaccination groups at the time of study enrolment, additional sensitivity analyses may adjust for imbalances in multivariable adjusted models.

Lastly, the presence of outliers will be evaluated using z-scores or boxplots for distributions, and if detected, sensitivity analyses may be performed excluding observations flagged as outliers.

## 9. REPORTING CONVENTIONS

P-values  $\geq 0.001$  and  $\leq 0.999$  will be reported to 3 decimal places; p-values less than 0.001 will be reported as “ $<0.001$ ” and p-values greater than 0.999 will be reported as  $>0.999$ . The mean, standard deviation, and other statistics will be reported to 1 decimal place greater than the original data. The minimum and maximum will use the same number of decimal places as the original data. Proportions will be presented as 2 decimal places; values greater than zero but less than 0.01 will be presented as “ $<0.01$ ” and values greater than 0.99 and less than one will be presented as “ $>0.99$ ”. Percentages will be reported to the nearest whole number; values greater than zero but  $< 1\%$  will be presented as “ $<1$ ”; values greater than 99% but less than 100% will be reported as  $>99\%$ . Estimated parameters, not on the same scale as raw observations (e.g., regression coefficients) will be reported to 3 significant figures unless otherwise specified in the output shells.

## **10. TECHNICAL DETAILS**

Clinical statistical analysis will be performed using Statistical Analysis Software (SAS®) version 9.4 (Cary, North Carolina, USA) and/or R version 4.0 or above. Other software may be used for processing of assays, and further details will be presented in the final report if they are available.

## **11. SUMMARY OF CHANGES IN THE CONDUCT OF THE STUDY OR PLANNED ANALYSES**

Any substantial changes to the analysis plan in the protocol prior to final database lock will be presented here. The SAP will be reviewed and updated prior to unblinding.

### 11.1 Interim Analysis Plan Alterations—December 2023

Additional content was added to section 5.6 to detail the expected analysis for the Interim Immunogenicity analysis. Blinded group analysis will be conducted for various immunologic parameters up through week 10 once all participants have been enrolled. Analysis of variance (ANOVA), non-parametric group tests, and group AUC will be used to assess the group short-term response. Adjustments for multiple comparisons, false discovery (FDR), and effect size (i.e. Bayes factors) will be used as appropriate.

## APPENDIX 1: ADDITIONAL TABLES AND FIGURES

**Table 1: Participant Disposition by Vaccination Group**

Participant Disposition	200 µg ALFQ (N=X)		100 µg ALFQ (N=X)		50 µg ALFQ (N=X)		All Participants (N=X)	
	n	%	n	%	n	%	n	%
Screened	--	--	--	--	--	--	--	--
Enrolled/Randomized	x	100	x	100	x	100	x	100
Received Study Vaccination Dose 1 (Visit 1, Day 1)	x	xx	x	xx	x	xx	x	xx
Completed Visit 2 (Day 15)	x	xx	x	xx	x	xx	x	xx
Received Study Vaccination Dose 2 (Visit 3, Day 29)	x	xx	x	xx	x	xx	x	xx
Completed Visit 4 (Day 43)	x	xx	x	xx	x	xx	x	xx
Received Study Vaccination Dose 3 (Visit 5, Day 57)	x	xx	x	xx	x	xx	x	xx
Completed Visit 6 (Day 58-9)	x	xx	x	xx	x	xx	x	xx
Completed Visit 7 (Day 64)	x	xx	x	xx	x	xx	x	xx
Completed Visit 8 (Day 71)	x	xx	x	xx	x	xx	x	xx
Completed Visit 9 (Day 169)	x	xx	x	xx	x	xx	x	xx
Completed Visit 10/Exit (Day 337)	x	xx	x	xx	x	xx	x	xx
Phone Follow-up #1 (Day 365)	x	xx	x	xx	x	xx	x	xx
Phone Follow-up #2 (Day 393)	x	xx	x	xx	x	xx	x	xx
Note: N = Number of randomized participants								

Table 2: Summary of Demographic and Baseline Characteristics by Vaccination Group

Variable	Characteristic	200 µg ALFQ (N=X)		100 µg ALFQ (N=X)		50 µg ALFQ (N=X)		All Participants (N=X)		p-value
		n	%	n	%	n	%	n	%	
Age	18-29	x	xx	x	xx	x	xx	x	xx	
	30-39									
	40-49									
	50+									
Age, years	Mean									
	Standard Deviation									
	Median									
	Q1 (25 th percentile)									
	Q2 (75 th Percentile)									
Gender	Male									
	Female									
	Transgender									
Sex at birth	Male									
	Female									
	Undifferentiated									
Level of Education										
	Primary education									
	Secondary education									
	Undergraduate degree									
	Graduate									
	Other									
Race	White									
	Black or African American									
	Asian									
	American Indian/Alaskan Native									
	Native Hawaiian or Other Pacific Islander									
	Multiracial									
	Other									
Ethnicity	Non-Hispanic/Latino									

Variable	Characteristic	200 µg ALFQ (N=X)		100 µg ALFQ (N=X)		50 µg ALFQ (N=X)		All Participants (N=X)		p-value
		n	%	n	%	n	%	n	%	
	Hispanic/Latino									

**Table 3: Summary of Participants with Pre-Existing Medical Conditions by Body System and Vaccination Group**

Body System	200 µg ALFQ (N=X)		100 µg ALFQ (N=X)		50 µg ALFQ (N=X)		All Participants (N=X)	
	n	%	n	%	n	%	n	%
General	X	X.X	X	X.X	X	X.X	X	X.X
HEENT	X	X.X	X	X.X	X	X.X	X	X.X
Cardiovascular								
Respiratory								
Gastrointestinal/Digestive								
Genitourinary								
Musculoskeletal								
Neurologic								
Endocrine								
Psychiatric								
Hematologic/Lymphatic								
Metabolic/Nutritional								
Allergy/Drug Sensitivity								
Other								

**Table 4: Distribution of Protocol Deviations by Deviation Category and Vaccination Group**

Deviation Category	200 µg ALFQ (N=X)		100 µg ALFQ (N=X)		50 µg ALFQ (N=X)		All Participants (N=X)	
	No. of Part.	No. of Dev.	No. of Part.	No. of Dev.	No. of Part.	No. of Dev.	No. of Part.	No. of Dev.
Enrollment	x	x	x	x	x	x	x	x
Informed consent	x	x	x	x	x	x	x	x
Visit schedule adherence	x	x	x	x	x	x	x	x
Protocol procedure	x	x	x	x	x	x	x	x
Adverse event not reported	x	x	x	x	x	x	x	x
Infusion schedule	x	x	x	x	x	x	x	x
Other	x	x	x	x	x	x	x	x

Note: Example categories and deviation types given

**SAFETY SUMMARY****Table 5: Overall Summary of Adverse Events**

	200 µg ALFQ (N=X)		100 µg ALFQ (N=X)		50 µg ALFQ (N=X)		All Participants (N=X)	
Participants a with	n	%	n	%	n	%	n	%
At least one local solicited reactogenicity event	X	X.X	X	X.X	X	X.X	X	X.X
Mild (Grade 1)								
Moderate (Grade 2)								
Severe (Grade 3)								
Potentially Life Threatening (Grade 4)								
At least one systemic solicited reactogenicity event	X	X.X	X	X.X	X	X.X	X	X.X
Mild (Grade 1)								
Moderate (Grade 2)								
Severe (Grade 3)								
Potentially Life Threatening (Grade 4)								
At least one unsolicited adverse event	X	X.X	X	X.X	X	X.X	X	X.X
At least one related unsolicited adverse event	X	X.X	X	X.X	X	X.X	X	X.X
Mild (Grade 1)	X	X.X	X	X.X	X	X.X	X	X.X
Moderate (Grade 2)	X	X.X	X	X.X	X	X.X	X	X.X
Severe (Grade 3)	X	X.X	X	X.X	X	X.X	X	X.X
Potentially Life Threatening (Grade 4)								
Fatal (Grade 5)								
At least one severe (Grade 3) unsolicited adverse event	X	X.X	X	X.X	X	X.X	X	X.X
Related	X	X.X	X	X.X	X	X.X	X	X.X
Unrelated	X	X.X	X	X.X	X	X.X	X	X.X
At least one adverse event of special interest	X	X.X	X	X.X	X	X.X	X	X.X
At least one serious adverse event b	X	X.X	X	X.X	X	X.X	X	X.X
At least one related, serious adverse event	X	X.X	X	X.X	X	X.X	X	X.X
At least one adverse event leading to early termination	X	X.X	X	X.X	X	X.X	X	X.X

**Table 6: Adverse Events Occurring in 5% of Participants in Any Vaccination Group by System Organ Class and Preferred Term, and Vaccination Group**

System Organ Class	Preferred Term	200 µg ALFQ (N=X)			100 µg ALFQ (N=X)			50 µg ALFQ (N=X)			All Participants (N=X)		
		n	%	Events	n	%	Events	n	%	Events	n	%	Events
Serious Adverse Events													
All	All	x	x.x	x	x	x.x	x	x	x.x	x	x	x.x	x
SOC 1	PT1	x	x.x	x	x	x.x	x	x	x.x	x	x	x.x	x
Etc.	Etc.												
Other (Non-Serious) Adverse Events													
All	All	x	x.x	x	x	x.x	x	x	x.x	x	x	x.x	x
SOC 1	PT1	x	x.x	x	x	x.x	x	x	x.x	x	x	x.x	x
Etc.	Etc												
Solicited Adverse Events													
All	All	x	x.x	x	x	x.x	x	x	x.x	x	x	x.x	x
SOC 1	PT1	x	x.x	x	x	x.x	x	x	x.x	x	x	x.x	x
Etc.	Etc												
Note: N = Number of participants in the Safety Population; n = Number of participants reporting event; Events = Total frequency of events reported.													

